SLE is a chronic inflammatory disease that has renal effect in about half of patients. Lupus nephritis is a major risk factor for morbidity and mortality in patients with SLE, and in spite of strong anti-inflammatory and immunosuppressive therapies still ends in CKD or ESRD. (5)

Based on this observation, we aim to determine the effect of SGLT2i treatment in patients with glomerulonephritis secondary to SLE who either is diabetic or non-diabetic.

Aim of the work

This study aims to assess SGT2i role in regression of ongoing kidney and cardiac diseases among lupus nephritis patient either diabetic or non-diabetic under different immunosuppressive therapy.

Patients and methods

Technical design:

Study sitting: .1

Nephrology and renal transplant unit at urology and nephrology center in Mansoura University.

It will include 100 patients with lupus nephritis, Diagnosis of glomerulonephritis was performed by renal biopsy, and all of the renal biopsies were carried out at urology and nephrology center.

Patients with an estimated glomerular filtration rate (eGFR) >30 ml/min/1.73m2 will be randomized into two groups

- Study group will receive SGLT2i inhibitor as add on drug or replace
 another drug according to patient clinical situation, Dapagliflozin 10
 mg and 25 mg will be used once daily with or without food.
 - Control group will be maintained on placebo. •

The primary endpoint will be sustained decline in eGFR ≥50%, ESKD, or kidney or cardiovascular death

We will follow up all patients for 12 months and compare their results.

2. Inclusion criteria:

- Patients aged more than 16 year. .1
- Willing to sign informed consent. .2
- Diagnosis of SLE according to EULAR/ACR classification .3 criteria.
 - Renal biopsy showed lupus nephritis. .4
- Patient with eGFR > 30 ml/min/1.73m2 by cockcroft-gault .5 equation.

3. Exclusion criteria:

- Patients with eGFR <30 ml/min per 1.73 m2. .1
 - Current pregnancy or lactation. .2
- Medical history of chronic disease (CLD, cancer, severe .3 respiratory distress, gastrointestinal tract lesions).
- Patients refusing to participate in the study or lost follow up. .4
- Evidence of urinary obstruction of difficulty in voiding at .5 screening.

- Patients who are receiving high dose diuretics or combined .6 ACEI, ARBS.
- Patients who have frequent hypotensive episode or SBP .7 <100 mmHg.

Operational design:

Study Protocol:

Patients included in the study will treated with dapaglifilozin

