 initiated at a total daily dosage of 10 mg/kg per day.

Study design:

Type of the study: randomized controlled study.

The following data will be gathered and evaluated for all patients:

I-before intervention:

- Serum creatinine, Creatinine clearance. .1
- 24 hour urine protein, urine protein/creatinine ratio. .2
 - Urine analysis. .3
 - HBA1c. .4
 - HGB. .5
 - Uric acid and lipid profile. .6
 - Lupus serology. .7

II-after intervention: All patients will be evaluated monthly regarding:

- Serum creatinine, creatinine clearance. .1
- 24 hour proteinuria, protein/creatinine ratio. .2
- Fasting, random and postprandial glucose levels. .3
 - CNI trough level if used. .4
 - Urine analysis. .5
 - HGB level. .6
 - Uric acid, lipid profile. .7
 - Lupus serology. .8

Cardiovascular assessment: .9

ECCHO.

Atherosclerosis and vascular calcification incidence (NCCT model).

Regular measurement of blood pressure each visit.

Outcomes:

- Effect of dapagliflozin compared to placebo on eGFR. .1
- Effect of dapagliflozin compared to placebo on systolic/diastolic blood .2 pressure.
 - Effect of dapagliflozin compared to placebo on body weight. .3
- Safety of dapagliflozin vs. placebo the number of hypoglycemia .4 episodes between groups and serious adverse events.

Statistical Analysis:

Qualitative data were displayed in cross tabulations, and quantitative data were described in terms of arithmetic mean ± SD. Bivariate techniques were used for initial evaluation of contrasts. Thus, the chi-square and Fisher's exact tests were used for comparisons of frequencies of qualitative variables; the Mann-Whitney test and the unpaired t-test were used for comparisons of means of two quantitative variables. A p-value <0.05 was considered significant. Graft and patient survival rates were assessed using the Kaplan-Meier method. All analyses were carried out using the computer package SPSS for windows, release 16 SPSS Inc. Chicago, III, USA.

Administrative design •

Informed consent will be obtained from all subjects and the approval will be obtained from institutional review board (IRB) in Faculty of Medicine, Mansoura University. There is no funding.

Research question

The main research question is: Does use of SGLT2i will show superiority over conventional lines of treatment of lupus nephritis patient as regard efficacy and safety.

Rationale and justification

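### The protocol's only time-to-event method is aimed at graft and patient survival, and neither protocol nor SAP assigns an analysis to the declared primary composite

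*Protocol*

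**What the plan says.** The protocol, under Technical design, states: "The primary endpoint will be sustained decline in eGFR ≥50%, ESKD, or kidney or cardiovascular death". It adds: "We will follow up all patients for 12 months and compare their results".

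Its Statistical Analysis section never mentions that composite. The one time-to-event sentence is "Graft and patient survival rates were assessed using the Kaplan-Meier method". For categorical data the same paragraph says "the chi-square and Fisher's exact tests were used for comparisons of frequencies of qualitative variables", and for quantitative data it names the t-test and the Mann-Whitney test.

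Grafts are absent from the rest of the protocol's design. The renal entry requirement is "Renal biopsy showed lupus nephritis", with an eGFR threshold; transplant is neither required nor excluded. The protocol's Outcomes list opens with "Effect of dapagliflozin compared to placebo on eGFR" and goes on to blood pressure, weight and safety. The composite is not on it.

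SAP section 4 makes creatinine, eGFR and 24-hour urine protein the primary renal endpoints, beside cardiac and haematological measures. SAP section 6 analyses creatinine and eGFR by repeated-measures ANOVA or the Friedman test. The SAP contains no survival method, and the composite does not appear in it.

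**The concern.** A primary endpoint needs a stated definition, a stated analysis and a stated comparison between arms. Here the composite has only its one-line description. There is no rule for what makes a decline sustained, no censoring rule, no treatment of deaths from other causes, and no log-rank, Cox or other comparison attached to it. The one survival analysis that is named points at a different outcome. Of the composite's components, all-cause patient survival touches only death, and without regard to cause.

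What is at stake is whether the protocol's primary question gets an answer at all and, if it does, whether the way events are counted was fixed in advance. As things stand, whether to look at the composite, what counts as an event and how to compare the arms are all left to choices made after the data are known.

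**Working it through.** **1. Does any section analyse the composite?**

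| Place | What it covers | Composite analysed? |
|---|---|---|
| Protocol, Technical design | Declares the composite; 12 months of follow-up | No method given |
| Protocol, Outcomes | eGFR, blood pressure, weight, safety | Not listed |
| Protocol, Statistical Analysis | General two-group tests; Kaplan-Meier for graft and patient survival | Not named |
| SAP sections 4 and 6 | Continuous renal, cardiac and haematological measures | Absent |
| SAP appended tables | Means, medians, side effects | No row for the composite, ESKD or death |

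The SAP's flow chart is not visible in the text available and could report deaths.

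**2. Could the data contain such events?** SAP Table 6 gives these creatinine maxima (mg/dL): control 2.7 at baseline, 4 at 9 months and 5 at 12 months; study 2.6, 4.2 and 5. The protocol's entry criterion uses Cockcroft-Gault, which varies inversely with creatinine when age and weight are fixed. A patient at 5 started no higher than the arm's baseline maximum, so:

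minimum fall = 1 − (baseline maximum ÷ later maximum)

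- Control, 12 months: 1 − 2.7/5 = 46%. Study: 1 − 2.6/5 = 48%.
- If the printed 5 was rounded from 4.5 and the baseline maxima were rounded down from 2.75 and 2.65: 1 − 2.75/4.5 = 39% and 1 − 2.65/4.5 = 41%.
- At 9 months: 1 − 2.7/4 = 32% and 1 − 2.6/4.2 = 38%.

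These are lower bounds, each for at least one patient per arm. They assume stable weight and age and the same patients at both visits. The true falls are larger if those patients did not start at the maximum.

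**3. How much could an analysis of the composite show?** SAP section 5 gives 100 patients and 80% power but no endpoint, effect size or event rate, so that figure cannot be reproduced. With 50 per arm and two-sided 0.05, 80% power corresponds to a standardised mean difference of (1.960 + 0.842) × √(2/50) = 0.56. That is a statement about a continuous outcome.

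For the composite, every rate and hazard ratio (HR) below is an assumption; the documents give none. Study-arm rate = 1 − (1 − control rate)^HR. Log-rank power ≈ Φ(|ln HR| × √events ÷ 2 − 1.96).

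| Control 12-month rate | Events, HR 0.6 | Log-rank power, HR 0.6 | Log-rank power, HR 0.5 |
|---|---|---|---|
| 2% | 1.6 | 5% | 6% |
| 5% | 4.0 | 7% | 10% |
| 10% | 8.1 | 11% | 16% |
| 20% | 16.3 | 18% | 27% |

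Example at 10% and HR 0.6: the study rate is 6.1%, events = 50 × 0.10 + 50 × 0.061 = 8.1, and power = Φ(0.511 × √8.06 ÷ 2 − 1.96) = Φ(−1.23) = 11%. By Schoenfeld's formula, 80% power at HR 0.6 needs 4 × (1.960 + 0.842)² ÷ (ln 0.6)² = 121 events. Exact Fisher power is at most 17% over the whole table.

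**The case against.** Three stronger readings are tempting, and the documents do not support them.

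*A reader might infer that no available method fits the composite.* The protocol does not call the endpoint a time to event. With 12 months of follow-up for everyone, occurrence by month 12 is a yes/no variable that the named chi-square or Fisher test could compare. That stands. The gap is that nothing directs those tests to the composite, and that the only survival method is directed elsewhere.

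*A reader might infer that real kidney events occurred and would go uncounted.* The protocol schedules creatinine under "All patients will be evaluated monthly regarding", so events could be derived, and patient survival would capture deaths. Table 6 does not prove an event either. Both lower bounds are under 50%. The value of 5 comes from the last visit, so it cannot be confirmed as sustained, and Table 10 reports acute kidney injury in 3 control and 7 study patients, so a transient peak is possible. The documents support less: no section requires kidney events to be defined or counted.

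*A reader might infer that transplant recipients were enrolled.* No criterion says so. The site is described as "Nephrology and renal transplant unit at urology and nephrology center in Mansoura University", and the SAP glossary lists death-censored graft failure, a term no SAP analysis uses. Text carried over from transplant work is the likelier explanation, though that is an inference.

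It can also be said that the SAP's continuous endpoints are now the real plan and that correcting one protocol sentence would change little. This is fair as far as it goes: the repair has to reach the SAP. But the SAP neither acknowledges nor explains the replacement, so it does not dispose of the point.

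**Conclusion.** The point holds in this form. The protocol declares a composite primary endpoint, names a time-to-event method only for an outcome this trial does not define, and attaches no between-arm comparison to it. The SAP drops the composite without comment. The plan as written therefore does not answer the protocol's primary question. That is a misdirected analysis, and more than missing detail.

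On size, Table 6 shows only that candidate events exist. At least one patient per arm lost about 46% (control) or 48% (study) of clearance or more, or about 39% and 41% allowing for rounding, under the assumptions stated above. Whether any fall reached 50%, or lasted, cannot be told.

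Naming a method would not make the composite well powered. At assumed control rates of 2% to 20% and HR 0.6, 100 patients give log-rank power of about 5% to 18%.

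**What to change.** Replace the graft-survival sentence with an analysis of the composite that states:

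- **Event derivation.** Derive kidney events from the scheduled creatinine measurements and require confirmation at the next scheduled measurement. The protocol plans monthly values but Table 6 shows three-monthly ones, so say which series is used.
- **Month 12.** Give a rule for declines first seen at the final visit: for example, class them as unconfirmed and show results with and without them.
- **Other definitions.** Define ESKD, how cause of death is attributed, and censoring.
- **Estimate and comparison.** Report 12-month cumulative incidence by arm with other deaths as a competing event, and a risk difference with exact 95% CI. Use a comparison suited to few events: Fisher's exact test, already named, or a log-rank test. Either is acceptable if chosen and stated.
- **Graft wording.** Delete it, or report how many enrolled patients had a transplant.

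Put the same analysis in the SAP, or record there that the primary endpoint was changed, with date and reason. The SAP is dated after the study period it reports and already carries results, so an analysis added now should be labelled as specified after the data were available.

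The cost is a short text change in both documents and a derivation from planned measurements. The downside is that few events are expected: the interval will be wide, power low, and the result must be reported as imprecise. A non-significant comparison should not be read as evidence of no effect.

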The rational of this study is that SGLT2i are now one of the common lines in regression of chronic kidney disease either is diabetic or not.

Large trials on this issue exclude patient with glomerulonephritis, so we will study its renal efficacy in patient with secondary glomerulonephritis to SLE to prove their efficacy and safety in this group of patients.

Objectives

The main objective of this study is to:

- To compare use of SGLT2i versus standard care in regression of chronic kidney disease in patient with LN.
 - To study the safety and efficacy of this drug group with use of immunosuppression and possible interaction.

Hypothesis

leading causes SLE is the one of the of secondary glomerulonephritis. Despite the use immunosuppressive and antiproteinuric drugs, a number of patients are at risk of progressing to end-stage kidney disease. Additional therapies to slow kidney function decline are highly desired. The DAPA-CKD trial demonstrated that the sodium glucose co-transporter 2 inhibitor dapagliflozin significantly reduced the risk of kidney failure and prolonged survival in participants with chronic kidney disease with and without type 2 diabetes. The DAPA-CKD population excluded patients with lupus nephritis, so we determined the long-term efficacy and safety of dapagliflozin on major

kidney and cardiovascular outcomes in these patients.

References

- James Matera, DO. SGLT2 Inhibitors and CKD in -1 2021. Consultant360. Published online May 25, 2021.
- Dan Xu, Owain Chandler, Cleo Wee, et al. Sodium--2
 Glucose Cotransporter-2 Inhibitor (SGLT2i) as a Primary
 Preventative Agent in the Healthy Individual: A Need of
 August 2021
- Hiddo J.L. Heerspink, Ph.D., Bergur V. Stefánsson, et-3al. Dapagliflozin in Patients with Chronic Kidney Disease.N Engl J Med 2020; 383:1436-1446.
- Kana N. Miyataa, Shao-Ling Zhanga John S.D. Chana-4. The Rationale and Evidence for SGLT2 Inhibitors as a-4Treatment for Nondiabetic Glomerular Disease.CJASN May 2017, 12 (5) 825-835.
- Salem Almaani, Alexa Meara and Brad H. -5 Rovin. Update on Lupus Nephritis Clin PharmacolTher 2007;81:228-34. 10.1038/sj.clpt.6100039.

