
General Considerations

Significance Level: A two-sided alpha level of 0.05 will be used for all primary analyses.

Analysis Populations:

Intent-to-Treat (ITT): All randomized patients will be analyzed according to their assigned group.

Per-Protocol (PP): Only patients completing the study without major protocol violations.

Primary Endpoint Analysis

Renal Outcomes: ANOVA for repeated measures for serum creatinine and eGFR if normally distributed, and the Friedman test for non-normally distributed data. Post-hoc tests using Bonferroni correction.

Cardiovascular Outcomes: Mann-Whitney U test for BNP levels and coronary calcification between groups.

Hematological Outcomes: Paired t-test for hemoglobin and erythropoietin levels if data is normally distributed; otherwise, Wilcoxon signed-rank test.

Secondary Endpoint Analysis

Body Weight and BMI: Compared over time using ANOVA for repeated measures.

Echocardiographic Parameters: Analyzed with paired t-tests, adjusted with Bonferroni correction.

Iron Profile: Analyzed pre- and post-intervention using ANOVA or Kruskal-Wallis for non-normally distributed variables.

Categorical Variables

Chi-Square Test: For between-group comparisons of categorical data (e.g., presence of diabetes, hypertension).

7. Handling of Missing Data

Imputation: Last observation carried forward (LOCF) for data missing at random; multiple imputation for extensive missing data.

Sensitivity Analysis: Conducted to evaluate the robustness of primary endpoint findings against different missing data assumptions.

8. Interim Analysis

Timing: An interim analysis is planned at the halfway point (6 months).

Stopping Rules: An O'Brien-Fleming approach will be applied to adjust the significance threshold for interim testing, allowing for an earlier stop for efficacy or safety concerns.

9. Safety Analysis

Adverse Events (AEs): Summarized by type, frequency, and severity. Fisher's exact test will be used to compare AE rates between groups.

Specific Safety Parameters: Monitoring for hypotension, electrolyte imbalances, and kidney function.

10. Data Quality and Management

Data Quality Measures: Includes data verification, regular audits, and query resolution.

Database Lock: Data will be locked and verified prior to the final analysis.

11. Software

Statistical Software: All analyses will be conducted using SPSS (Version 25).

12. Appendices

	Control group. (n= 41)	Study group. (n= 38)	P value

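### The protocol sets out to prove safety, but safety is compared only by difference tests, with no interval, upper bound or margin for harm

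*Protocol*

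**What the plan says.** - **Aim.** The protocol's Rationale and justification says the drug will be studied "to prove their efficacy and safety in this group of patients". Its Research question asks whether SGLT2i will "show superiority over conventional lines of treatment of lupus nephritis patient as regard efficacy and safety". Safety is also named in the Objectives.
- **Safety outcome.** Protocol Outcomes, item 4, reads "Safety of dapagliflozin vs. placebo the number of hypoglycemia", continuing "episodes between groups and serious adverse events".
- **Tests.** SAP section 9 summarises adverse events and adds that "Fisher's exact test will be used to compare AE rates between groups". The protocol's Statistical Analysis says "the chi-square and Fisher's exact tests were used for comparisons of frequencies of qualitative variables". The footnote to SAP Table 10 cites chi-square.
- **Threshold.** The protocol says "A p-value <0.05 was considered significant". The SAP's own statement is narrower: "A two-sided alpha level of 0.05 will be used for all primary analyses".
- **Interim.** SAP section 8 applies an O'Brien-Fleming approach at 6 months and allows a stop for safety, but names no safety endpoint and gives no boundary value.
- **Not given anywhere.** A confidence interval or upper bound for harm, an acceptable excess risk, or a safety event rate behind the sample size.

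**The concern.** A difference test can give evidence that the drug raises, or lowers, the rate of an event. When it is not significant, it does not say how large an increase remains possible. In a trial of this size that increase can be large.

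The protocol makes safety one of the things to be proved, yet the analysis yields only a p-value for each event. A reader of the final tables would have no planned figure for the excess harm that the data leave open, and nothing in the SAP warns against taking non-significance as reassurance. What is at stake is how far the trial's safety statement can go, in a population that the protocol says the large trials left out.

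**Working it through.** **1. The plan's own figure.** SAP section 5 gives 100 patients for 80% power at 0.05. It cannot be reproduced, because no endpoint, effect size, SD, event rate or dropout percentage is stated. Inverted for a two-group comparison of means, detectable standardised difference = (1.960 + 0.842) × √(1/n₁ + 1/n₂):

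- 50/50: 2.802 × √(2/50) = 0.56
- 41/38: 2.802 × √(1/41 + 1/38) = 0.63

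No safety rate enters the stated calculation, so the 80% says nothing about harms.

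**2. Inputs for the safety check.**

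- Arm sizes: 50/50 (100 patients at 1:1, SAP sections 2 and 5) and 41 control / 38 study (Table 10).
- AKI, Table 10: control 1 + 2 = 3 of 41 (7.3%); study 5 + 2 = 7 of 38 (18.4%).
- Urinary tract infection (UTI), Table 10: control 4 + 2 = 6 of 41 (14.6%); study 5 + 2 = 7 of 38 (18.4%).
- Other control rates (5%, 10%, 20%) are assumptions, shown as a range.
- Each patient counts once, as having or not having the event. Alpha is 0.05 two-sided. For adverse events the 0.05 comes from the protocol's general rule and two-sidedness is assumed.

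**3. Power of Fisher's exact test.** For control risk p and study risk kp, power is the sum of Bin(a; n₁, p) × Bin(b; n₂, kp) over all 2×2 tables with two-sided Fisher p<0.05 and the higher rate in the study arm.

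| Control rate | Doubling, 50/50 | Doubling, 41/38 | Tripling, 50/50 | Tripling, 41/38 |
|---|---|---|---|---|
| 5% | 6% | 10% | 24% | 26% |
| 7.3% (AKI) | 12% | 14% | 43% | 41% |
| 10% | 19% | 19% | 64% | 56% |
| 14.6% (UTI) | 34% | 29% | 88% | 80% |
| 20% | 52% | 44% | 98% | 96% |

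The AKI tripling figure at 50/50 is 43.5% before rounding. Power first reaches 50% for a doubling at a control rate of 19.6% (50/50) or 21.9% (41/38), and for a tripling at 8.2% or 8.9%. At a 7.3% control rate, 80% power needs a risk ratio of about 4.1 (50/50) or 4.5 (41/38).

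**4. What the tabulated data leave open.** Newcombe's 95% CI combines the Wilson limits (l, u) of each arm. Lower = d − √[(p₁−l₁)² + (u₂−p₂)²]; upper = d + √[(u₁−p₁)² + (p₂−l₂)²].

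- AKI: p₁ = 0.184 (Wilson 0.092 to 0.334), p₂ = 0.073 (0.025 to 0.194), d = 0.111. Lower = 0.111 − √(0.092² + 0.121²) = −0.041. Upper = 0.111 + √(0.150² + 0.048²) = 0.269. Fisher p=0.18; risk ratio 2.5 (95% CI 0.70 to 9.0).
- UTI: d = +3.8 points, 95% CI −12.8 to +20.7. Fisher p=0.76.

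Both results are non-significant, yet the upper limits are about 27 and 21 percentage points.

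**5. If an event is not seen at all.** For 0 of 38, the exact one-sided 95% upper bound is 1 − 0.05^(1/38) = 7.6%; the two-sided limit is 1 − 0.025^(1/38) = 9.3%.

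**The case against.** The case against has real force.

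- **Nothing in the documents says that p>0.05 means safe.** The Research question is one of superiority, for which a difference test is the matching tool and the route to a claim is p<0.05 in the drug's favour. The Objectives only speak of studying safety, SAP section 9 starts with description, and Table 10 draws no conclusion. A reader might infer that the trial would go on to report safety as proven. That is a prediction, and the documents do not support it.
- **A reader might infer that Fisher's test is the only safety rule.** It is not. The protocol also names chi-square, and SAP section 8 allows an interim stop for safety. Neither, as written, bounds the excess harm.
- **A reader might infer that a tripling would usually be missed whatever the event.** That fails for common events: at the Table 10 UTI rate a tripling is found about 80-88% of the time, and at 10% it is found more often than not.
- **A reader might infer from their absence in Table 10 that no hypoglycemia or serious adverse events occurred.** The table shows only that they were not tabulated there. The 0/38 bound is an illustration.
- **Low power for rare harms is common to small trials**, and the protocol's hypoglycemia outcome is a count of episodes, which a yes/no calculation only approximates.

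These points limit the claim but do not remove it. Proving safety remains a stated aim, and the plan provides no analysis that could support it short of showing significantly fewer events on the drug.

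**Conclusion.** The point holds in a limited form. The safety comparisons are difference tests with no interval, upper bound or margin, so a non-significant result cannot support the aim in the rationale. A doubling of risk is missed more often than not at control rates below about 20-22%, and a tripling only below about 8-9%. The trial's own AKI figures show the consequence: non-significant, but compatible with an excess of up to about 27 points.

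The power figures rest on one event indicator per patient, a two-sided 0.05 level for adverse events, arm sizes of 50/50 or 41/38, and control rates taken from Table 10 or assumed. The absence of an interval or bound does not depend on any of these. This is an inexpensive improvement to the analysis and reporting. It is not evidence that the drug is harmful, nor that the investigators have claimed it is safe.

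**What to change.** 1. In SAP section 9, base the safety statement on the drug-minus-placebo risk difference with a 95% CI (Newcombe, for example) for patients with hypoglycemia, for patients with serious adverse events, and for each adverse event type. Quote the upper limit as the excess not ruled out. Fisher's p-value can stay alongside.
2. Where an arm has no events, report 0/n with the exact upper bound.
3. State in SAP section 9 that a non-significant p-value is not evidence of safety.
4. In the protocol rationale, change the aim from proving efficacy and safety to assessing efficacy and describing safety.
5. Optional, and the sponsor's choice: if a positive safety claim is wanted for an event, state and justify a margin and make the claim only when the upper limit lies below it.

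**Cost.** Wording changes in two documents and a few more intervals, with no new patients or procedures. The drawback is a weaker safety conclusion than the rationale promises.
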